6.12.2. Additional Analyses of the Primary Outcome

The primary efficacy analysis will be repeated with a per-protocol analysis set including only those subjects who completed the study with no major protocol deviations to verify robustness of the results.

6.12.3. Secondary Efficacy Analyses

The secondary efficacy outcomes (PDAQ-15, ADAS-Cog₁₃, CDR-CCB PoA, D-KEFS, MoCA, NPI, ESS, and MDS-UPDRS) will be assessed at the 12-week time point as the primary analysis. Each of these secondary endpoints will be analyzed using a frequentist MMRM model, which will include terms for: baseline value, treatment, visit, age, concomitant use of AChEIs, and the relevant interaction terms (treatment by visit, baseline by visit). The change in score from baseline will be the dependent variable. If subscores for a particular scale are deemed clinically relevant to analysis, it will be completed as an exploratory analysis.

For the Alzheimer’s Disease Cooperative Study – Clinician Global Impression of Change (ADCS-CGIC), a logistic regression analysis will be performed with treatment, visit, age, concomitant medication of AChEIs, and relevant interaction terms. Two different endpoints will be assessed: “moderately or better,” defined as subjects who had moderate/marked improvement and “minimally or better” defined as subjects who had minimal/moderate/marked improvement on the ADCS-CGIC scale.

Levodopa equivalency dose (LED) will be calculated using the conversion factors (Tomlinson et al. 2010) of the actual daily dose (mg) of the relevant PD drugs (Table HBEH.6.1). After the LED is calculated for each concomitant medication that a subject is taking, the total LED will be used as a covariate for the analyses of the MDS-UPDRS scales. The impact of LED may be explored for various efficacy and safety measures.

Table HBEH.6.1. LED Conversion Factors

Medication	Multiplication Factor
Immediate release L-dopa dose	1
Controlled release L-dopa dose	0.75
*Entacapone	LD × 0.33
*Tolcapone	LD × 0.5
Duodopa	1.11
Pramipexole (as salt)	100
Ropinirole	20
Rotigotine	30
Selegiline – oral	10
Selegiline – sublingual	80
Rasagiline	100
Amantadine	1
Apomorphine	10

Abbreviation: LED = levodopa equivalency dose.

Note: *LD represents immediate release L-dopa dose for particular patient.

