All subjects in the evaluable patient population (EPP) will be considered for the efficacy analysis. The primary analysis on CoA will occur when all subjects complete 12 weeks of treatment. The analysis of CoA will utilize a Bayesian MMRM model. The Bayesian analysis may use uninformative priors for all terms in the model. These will be diffuse Normal distributions centered on zero. Priors for variance will follow an inverse gamma distribution. Further details of the Bayesian analysis will be provided in the SAP. The MMRM model will account for longitudinal data assessed throughout the study, after 1, 2, 4, 6, 8, 10, and 12 weeks of dosing. The change of CoA from the baseline to Week 12 will be the dependent variable.

The model will comprise fixed (baseline value, treatment, visit) and random effects (subject) and the interaction terms (treatment by visit, baseline value by visit). Unstructured variance structure will be applied in the model, but if it fails to converge, other suitable structures will be investigated. The primary comparison will be the contrast (difference in least squares mean) between treatments and placebo for the Week 12 change from baseline.

The secondary efficacy outcomes: the change from baseline at 12-week time point of total scores (or composite values) of Alzheimer's Disease Cooperative Study – Clinician Global Impression of Change (ADCS-CGIC), CDR-CCB Power of Attention (PoA), 13-item Alzheimer's Disease Assessment Scale – Cognitive subscale (ADAS-Cog₁₃), Montreal Cognitive Assessment (MoCA), Neuropsychiatric Inventory (NPI), Epworth Sleepiness Scale (ESS), Movement Disorder Society's Unified Parkinson's Disease Rating Scale (MDS-UPDRS), Penn Parkinson's Daily Activities Questionnaire 15 (PDAQ-15), and Delis–Kaplan Executive Function System (D-KEFS) will follow the same analysis method as above.

Missing records in some scales (e.g., ADAS-Cog) will be imputed as detailed in the statistical analysis plan. For the scales where the imputation is not done, if any item is missing, any total or sum involving that item will be considered missing. No adjustment for multiple comparisons will be made.

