10.3.3.2. Secondary Efficacy Analyses

The secondary efficacy outcomes (ADCS-CGIC, PDAQ-15, ADAS-Cog₁₃, CDR-CCB PoA, D-KEFS, MoCA, NPI, ESS, and MDS-UPDRS [total and Part III]) will be assessed at the 12-week time point. Each of these secondary endpoints will be analyzed using an MMRM model, which will include terms for: baseline value, treatment, visit, and the relevant interaction terms. Further covariates may be included such as age, site, and the severity of PD motor function as well as severity of dementia at baseline as appropriate. The change of the score from baseline will be the dependent variable. If subscores for a particular scale are deemed clinically relevant to analysis, it will be completed as an exploratory analysis.

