Appendix 1. Potentially Clinically Significant Vital Signs34

3. Revision History

SAP Version 1 was approved prior to unblinding.

SAP Version 2 was approved prior to unblinding and includes updates from Amendment (b) and information on coronavirus disease 2019 (COVID-19) impact.

SAP Version 3 was approved after unblinding. The overall changes and rationale for the changes incorporated in Version 3 are as follows:

- Edits were made to comply with ALCOA+++ principles.
- Administrative changes (not affecting content), such as correcting typographical and formatting errors, were made.

4. Study Objectives

Table HBEH.4.1 shows the objectives and endpoints of the study.

Table HBEH.4.1. Objectives and Endpoints

Objectives	Endpoints

Primary To test the hypothesis that LY3154207 administered at 10 mg, 30 mg, and/or 75 mg daily (or 50 mg based on interim analysis) (QD) oral dosing for 12 weeks will result in a significant improvement in cognition in subjects with mild-to-moderate LBD compared with placebo.
	
Change in the CoA composite score of the CDR-CCB from baseline to Week 12

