
Secondary Efficacy: To evaluate the global efficacy of LY3154207
 
To evaluate the efficacy of LY3154207 on cognitive outcomes
 
To evaluate the efficacy of LY3154207 on cognitive outcomes
 
To evaluate the efficacy of LY3154207 on cognitive outcomes
 
To evaluate the efficacy of LY3154207 on neuropsychiatric symptoms
 
To evaluate the effect of LY3154207 on daytime sleepiness
 
To evaluate the effect of LY3154207 on Parkinson's disease severity
 
To evaluate the efficacy of LY3154207 on functional outcome
 
To evaluate the effect of LY3154207 on verbal fluency
 
To evaluate the effect of LY3154207 on motor symptoms and signs
	
ADCS-CGIC score from baseline to Week 12
 
Change in the CDR-CCB PoA composite score from baseline to Week 12
 
Change in the ADAS-Cog₁₃ score from baseline to Week 12
 
Change in the MoCA score from screening to Week 12
 
Change in the NPI total and individual items scores from baseline to Week 12
 
Change in the ESS score from baseline to Week 12
 
Change in the MDS-UPDRS total score (sum of parts I-III) from baseline to Week 12
 
Change in the PDAQ-15 total score from baseline to Week 12
 
Change in D-KEFS Verbal Fluency test score from baseline to Week 12
 
Change in MDS-UPDRS Parts II (motor experiences of daily living) and III (motor exam) from baseline to Week 12

Objectives and Endpoints

Objectives	Endpoints

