Longitudinal analyses from baseline to Week 12 will use the change from baseline score as the response variable. An unstructured covariance matrix will be considered for MMRM; however, if this fails to converge, other structures will be considered based on the trial design. Unless stated otherwise, for all MMRM analyses, the difference in least squares (LS) means between LY3154207 and placebo, corresponding 95% credible or CIs, and p-values will be presented.

Any change to the data analysis methods described in the protocol will require an amendment ONLY if it changes a principal feature of the protocol. Any other change to the data analysis methods described in the protocol, and the justification for making the change, will be described in the clinical study report (CSR).

Only key analyses and results relating to primary and secondary objectives will be presented in the CSR. Exploratory and sensitivity analyses are not expected to be included in the CSR, unless they are relevant to the trial conclusions. Further exploratory analyses, in addition to those specified in this SAP may be conducted, if deemed appropriate.

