6.7. Multiple Comparisons/Multiplicity

No adjustments will be made for multiple comparisons.

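### SAP 6.12.3 analyses ADCS-CGIC only as two improvement cuts, so the 7-point score named as the sole global efficacy endpoint has no usable planned analysis

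*SAP*

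**What the plan says.** SAP Table HBEH.4.1 has one objective on global efficacy. Its endpoint is "ADCS-CGIC score from baseline to Week 12", with no responder definition.

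Protocol 10.3.3.2 lists ADCS-CGIC among the secondary outcomes and states: "Each of these secondary endpoints will be analyzed using an MMRM model". That model has a baseline value as covariate and change from baseline as response. The protocol synopsis also lists ADCS-CGIC among the secondary outcomes that "will follow the same analysis method as above", meaning the primary model.

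SAP 6.12.3 omits ADCS-CGIC from its MMRM list. For this scale alone, "a logistic regression analysis will be performed with treatment, visit, age, concomitant medication of AChEIs, and relevant interaction terms". Two outcomes are fitted. The moderate cut counts scores 1-2 as success. The minimal cut counts scores 1-3 and is "defined as subjects who had minimal/moderate/marked improvement on the ADCS-CGIC scale".

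SAP 6.12.4 (exploratory) and 6.12.5 (sensitivity) add no ordinal, rank or mean-score analysis of ADCS-CGIC. SAP 6.15 says that CGIC may be examined in subgroups with the model of 6.12.1.

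**The concern.** The named endpoint is a 7-point score, but the planned analysis uses only whether the score lies on the improved side of a cut. Score 4 (no change) and scores 5-7 (worsening) count as the same result in both cuts. A dose that mainly prevents worsening therefore cannot show on the trial's only global measure, and a general shift is detected with less power than the collected rating allows.

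Some departure from the protocol model was needed. Protocol 9.1.2.1.1 describes ADCS-CGIC as itself a rating of change, and the Schedule of Activities has only an interview at Visit 2, with ratings at Visits 8 and 11 and at early termination. There is no baseline score to adjust for or subtract. SAP 6.12.3 avoids that problem but loses the score in doing so, and SAP 6.15 brings the problem back.

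Under SAP 6.12.7, ADCS-CGIC could be collected by telephone during the pandemic, whereas CoA is missing at every virtual visit. Full use of the rating is worth more for that reason.

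**Working it through.** **Text.** These are the places where the plan could analyse the ADCS-CGIC score:

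| Place | What it offers | Usable for the score? |
|---|---|---|
| Protocol 10.3.3.2 and synopsis | MMRM with baseline value, change from baseline | Not as written: no baseline score |
| SAP 6.12.3 | Two logistic regressions on cuts | No: not the score |
| SAP 6.12.4, 6.12.5 | Nothing on ADCS-CGIC | No |
| SAP 6.15 | Optional, subgroups, 6.12.1 model (baseline, baseline by visit, change from baseline) | Not as written |

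**Plan's own figure.** There is none for ADCS-CGIC. The probability of over 80% in Protocol 10.1 concerns CoA, with a criterion that is blacked out.

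**Inputs.** 85 per arm less 20% discontinuation (Protocol 5.2, 10.1): 85 × 0.8 = 68. Effect 0.4 SD = 7.2/18, borrowed from CoA planning. Two-sided 5%. The placebo distributions over scores 1 to 7 are assumptions (%):

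- A 2/8/20/40/20/8/2
- B 1/4/15/60/15/4/1
- C 3/12/35/30/14/5/1
- D 1/4/10/40/30/12/3
- E 8/22/30/27/9/3/1
- F 0.5/2.5/47/47/2/0.7/0.3

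**Information.** For a shift on a latent normal scale, information = Σ (difference in φ between the category's two cut points)² / category probability. For A, φ at the cumulative points 0.02, 0.10 and 0.30 is 0.0484, 0.1755 and 0.3477, and the distribution is symmetric.

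- Seven categories: 2 × (0.0484²/0.02 + 0.1271²/0.08 + 0.1722²/0.20) = 0.935
- Minimal cut: 0.3477²/(0.30 × 0.70) = 0.576, a loss of 1 − 0.576/0.935 = 38%
- Moderate cut: 0.1755²/(0.10 × 0.90) = 0.342, a loss of 1 − 0.342/0.935 = 63%

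**Power at 0.4 SD.** 20,000 simulated trials per setting, one visit, unadjusted; tie-corrected rank test on the score, likelihood-ratio test on each cut. Simulation error is about 1 point.

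| | Placebo worse % | Loss, minimal % | Loss, moderate % | Loss, both jointly % | Power, score (rank) % | Power, minimal % | Power, moderate % |
|---|---|---|---|---|---|---|---|
| A | 30 | 38 | 63 | 33 | 59 | 44 | 32 |
| B | 20 | 42 | 74 | 39 | 56 | 40 | 25 |
| C | 20 | 32 | 54 | 19 | 60 | 45 | 37 |
| D | 45 | 54 | 76 | 52 | 59 | 37 | 26 |
| E | 13 | 34 | 39 | 17 | 59 | 44 | 44 |
| F | 3 | 18 | 80 | 10 | 52 | 45 | 23 |

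The joint column is a lower bound on the loss, because the SAP fits the cuts separately. A t test or a proportional-odds model on the score gives 53-61%. For the score, minimal cut and moderate cut respectively, power is 32-40%, 22-28% and 17-28% at 0.3 SD, and 71-80%, 55-63% and 32-62% at 0.5 SD.

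**Less worsening only.** Move half of scores 5-7 to score 4. In A, worsening falls from 30% to 15% and no change rises from 40% to 55%; the cuts stay at 30% and 10%. The true difference on each cut is exactly zero, so they reject at their null rate (5-9%). The score (t test or proportional odds) rejects 44-57% when 45% of placebo subjects worsen (D), 20-21% at 30% (A), 8-16% at 20% (B, C) and 5-7% at 13% or fewer (E, F).

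**The case against.** The cuts are legitimate. The stated hypothesis is improvement, and Protocol 9.1.2.1.1 ties moderate change to an effect on clinical status, so the moderate cut has a documented meaning. This stands: the fault is only that the cuts are the whole analysis.

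The protocol and SAP 6.15 do treat CGIC as a score, and SAP 6.2 and 6.12.4 allow further exploratory analyses. But both models call for a baseline that does not exist, 6.15 is optional and limited to subgroups, and a general permission does not prespecify an analysis of a named endpoint.

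Less decline is visible elsewhere, because CoA, ADAS-Cog13, PDAQ-15 and other scales are analysed in full by MMRM. This is true and limits the stakes. It does not help the global rating.

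Testing both cuts might be said to recover the power. A win on either gives 46-60% at 0.4 SD, but it rejects 9-14% under the null with likelihood-ratio tests, and SAP 6.7 says "No adjustments will be made for multiple comparisons". The upper end of that range owes something to the test: at event rates of 3-5% the likelihood-ratio test is liberal, and with a Pearson chi-square the rate is about 9%. The SAP also states no rule of winning on either cut. The finding does not depend on this figure.

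Finally, every power figure rests on assumed distributions, a borrowed effect size and an unadjusted single-visit comparison. The gain over the minimal cut is about 15-22 points in A-E but only 7 in F.

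**Conclusion.** The concern holds. As written, the documents contain no workable overall analysis of the ADCS-CGIC score, although the SAP names that score as its only global efficacy endpoint, and 6.15 sends CGIC to a model that cannot be fitted to it. Under the six assumed distributions the minimal cut loses 18-54% of the information in the score and the moderate cut 39-80%. Neither cut can register a difference confined to scores 4-7; the gain from the score for that kind of effect is large only if many placebo subjects worsen. The consequence is weaker and partly blind evidence on one secondary endpoint of an exploratory study. The primary conclusion is not touched, and the point does not rest on type I error of the Week 12 contrast. The plan should be corrected because the remedy is cheap.

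**What to change.** Add to SAP 6.12.3 an analysis of the 7-point score with a Week 12 contrast of each dose against placebo. Either a longitudinal proportional-odds model or an MMRM on the score would serve, with treatment, visit, treatment by visit, age and AChEI use, and no baseline-score term.

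Keep both responder cuts, with a Week 12 contrast. Since that model has a visit term and subjects are rated at Visits 8 and 11, state how within-subject correlation is handled (GEE or mixed logistic regression); 6.12.3 names no method.

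In SAP 6.15, replace the 6.12.1 model for CGIC with the same score model.

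SAP Section 3 records that "SAP Version 3 was approved after unblinding". A score analysis introduced now must be labelled as added after unblinding, and the departure from the protocol's MMRM should be justified in the CSR, as SAP 6.2 requires for such changes.

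The cost is one standard model on data already collected and wording in two sections. A late addition carries less weight than a prespecified one. An odds ratio or mean shift is also harder to read than a responder rate, which the retained cuts supply.

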6.12.4. Tertiary/Exploratory Efficacy Analyses

The following exploratory efficacy endpoints will be analyzed using an MMRM model:

- change in the total score for the ADAS-Cog₁₁ from baseline to Week 12 (a subset of ADAS-Cog₁₃)
- change in the CDR-CCB Cognitive reaction time composite score, Reaction Time Variability composite score, and Attention Ratio and Speed Score composite scores from baseline to Week 12
- change in the CDR-CCB individual task outcomes from baseline to Week 12 including simple reaction time, digit vigilance, choice reaction time, numeric working memory, spatial working memory, verbal memory, and visual memory
- change in total MDS-UPDRS (sum of Part I-III) and individual subscales non-motor experiences of daily living (Part I), motor experiences of daily living (Part II), motor exam (Part III), and motor complications (Part IV) subscales from baseline to Week 12

- change in items 4.3 through 4.6 (time off, impact of off, complexity of off, off dystonia) of the MDS-UPDRS from baseline to Week 12
- change in NPI score (Part D Depression/Dysphoria) from baseline to Week 12, and
- change in Geriatric Depression Scale (GDS) total score from baseline to Week 12.

Where appropriate, further exploratory analyses will be completed.

6.12.5. Sensitivity Analyses

A frequentist MMRM analysis of the primary analysis will be conducted.

An alternative MMRM analysis of change in CoA from baseline to Week 12, using the average change from baseline over Week 6 to Week 12 as the response variable, may also be considered. If there is a treatment difference prior to Week 12, which remains through to Week 12, this approach may be more sensitive than just looking at Week 12.

If baseline values are imputed from screening values in the primary analysis of CoA, a sensitivity analysis will be conducted to compare this approach with excluding subjects with missing baseline scores.

Differences in baseline characteristics of the treatment groups may be investigated using the Chi-squared test and 2 sample t-tests for categorical and continuous variables, respectively, if appropriate.

6.12.6. Dose Response Modeling

Dose response modeling may be utilized to understand the dose response relationship of select efficacy and safety measures including CoA, ADAS-Cog, MDS-UPDRS, SBP, diastolic blood pressure (DBP), and PR.

A trend test may be completed to assess evidence of a dose response by fitting a contrast statement in the MMRM model. In its simplest form, the analysis assigns equally spaced coefficients in the contrast, that sum to zero across the levels of the treatment factor (for example, -3, -1, 1, 3). This analysis assumes that the change in benefit from 75 mg compared to 30 mg is equivalent to the change from 30 mg to 10 mg and 10 mg to placebo. Alternative coefficients may be used if this assumption is inappropriate.

A Bayesian model averaging approach may be used to estimate the dose response relationship. This Bayesian model averaging approach is the Bayesian analog of the Multiple Comparison Procedure – Modeling (MCP-Mod) methodology (Bretz et al. 2005), and the Qualification of the MCP-Mod procedure (FDA 2015) is supportive in the use of MCP-Mod or Bayesian model averaging to assist in dose selection decisions.

Bayesian model averaging is a general mixture distribution, where each mixture component is a different parametric model. Prior weights are placed on each model and the posterior model weights are updated based on how well each model fits the data. Let $\mu(d)$ represent the mean of the dose response curve at dose d , $y = \{y_1, \dots, y_n\}$ be the observed data, and $m \in \{1, \dots, M\}$ be

an index on the M parametric models. Then the posterior of the dose response curve, $\mu(d)$, of the Bayesian model averaging model is

$$p(\mu(d) | y) = \sum_{m=1}^M p(\mu(d) | y, m) p(m | y)$$

$$p(m | y) = \frac{p(y | m)p(m)}{\sum_{m^*} p(y | m^*)p(m^*)}$$

where $p(\mu(d) | y, m)$ is the posterior mean dose response curve from model m , $p(m | y)$ is the posterior weight of model m , $p(y | m)$ is the marginal likelihood of the data under model m , and $p(m)$ is the prior weight assigned to model m . In cases where $p(y | m)$ is difficult to compute, Gould (2019) proposes using the observed data's fit to the posterior predictive distribution as a surrogate in calculating the posterior weights; this is the approach used in this analysis.

Potential candidate models that will be used are quadratic, log-quadratic, linear, log-linear, and EMAX models.

6.12.7. COVID-19

Due to the COVID-19 pandemic quarantine and travel restrictions, alternative methods of collecting key efficacy and safety data were implemented to allow subjects to safely remain in the trial.

Beginning in March 2020, enrolled subjects unable to attend in-person clinic visits due to COVID-19 restrictions were able to continue in the study by replacing in-person visits with telephone visits. All subjects had to have access to investigational product and an HBPM device to participate in the study remotely. During the telephone visits, investigators collected vital signs using the HBPM, AEs, concomitant medications, and the relevant information from the Columbia-Suicide Severity Rating Scale (C-SSRS). Additional efficacy outcomes were also collected, at appropriate visits, by phone and included the ADCS-CGIC, D-KEFS, PDAQ-15, MDS-UPDRS Parts I/II/IV, NPI, Questionnaire for Impulsive-Compulsive Disorders in Parkinson's Disease (QUIP), Geriatric Depression Scale – Short Form (GDS-S), ESS, and physician withdrawal checklist-20 (PWC-20). In April 2020, the study implemented an option to allow web-based videoconference visits to assess additional measures that required visual inspection: the ADAS-Cog13, MDS-UPDRS Part III, and MoCA. The primary outcome, CDR-CCB CoA, was not collected remotely and is missing for all virtual visits. Visits conducted via telephone and/or video were documented within the study database. Given the variability in modality of collection among subjects, visits, and scales, sensitivity analyses will be conducted on the relevant scales excluding data collected via virtual visits.

Missingness due to COVID-19 does not depend on the outcome measurements and therefore will still be considered MAR. The MMRM analyses approach can handle missing values.

Since there is no anticipated interruption or discontinuation of treatment, the definition of an intercurrent event remains unchanged.

Additionally, a COVID-19 impacted population will include any subject after 01 March 2020 who had at least 1 virtual visit. This will allow for a variety of exploratory analyses regarding the impact of COVID-19 and mitigation strategies.

